Official Title: Follicle Activation in Patients with Poor Ovarian Response Through Fragmentation of the Ovarian Tissue.

ClinicalTrials.gov.ID: NCT02354963

Document date: 10th April 2022

Statistical Analysis Plan

Statistical Analysis Plan

The allocation of patients to the study groups was performed using a random number generator (www.random.org), the numbers generated were included in a sealed envelope that was opened at the time of patient randomization.

Information on study variables was collected in a data record booklet (DRB) designed specifically for this study. A database was created to contain the information from the CRFs of the included patients and was equipped with internal consistency rules to control for inconsistencies and/or inaccuracies in data collection and tabulation. The internal coherence rules were guaranteed based on index fields that avoid duplicate records, detect out-of-range or suspicious data and prevent the recording of unrelated data. Before the computerization of the data, a thorough review of the data CRFs was carried out to ensure maximum reliability of the record.

Statistical analysis was performed with the SPSS 2.0.0 statistical package. Variables that followed a normal distribution were expressed as mean and standard deviation, and variables that did not follow a normal distribution were described as median and range. Categorical variables were expressed as absolute values and percentages. Observed differences were considered statistically significant if $p < 0.05$. Comparison of quantitative variables was performed using the Student's t-test or U-Mann test, as appropriate. Comparison of categorical variables was performed using the Chi-square or Fisher test, as appropriate.

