The fragmentation of the ovarian cortex in vitro activates the growth of primordial follicles, leading to the appearance of a greater number of antral follicles, which would make it possible to obtain more oocytes after controlled ovarian stimulation in patients with low ovarian response, which would be useful for improving the success rate of IVF in patients with low ovarian response.

3. Objectives

Main objective:

- To assess whether the fragmentation of ovarian cortex increases the pool of antral (potentially stimulable) follicles.

Secondary objectives:

- To analyse whether the proposed intervention improves ovarian response after gonadotrophin stimulation.
- To evaluate the pregnancy rate.

4. Study design

TYPE OF STUDY

Two-phase study:

- Phase 1: Randomised, controlled, single-blinded clinical trial. Sixty patients previously confirmed as low responders according to ESHRE criteria will be randomised to two treatment arms after assessment of ovarian reserve:

- Arm 1 (control): no intervention was performed on the patient.
- Arm 2 (intervention): removal of ovarian cortex by unilateral laparoscopic oophorectomy, fragmentation of ovarian tissue into 2 mm² aliquots. The ovarian tissue was then re-transplanted under the serosa of the tube homolateral to where the cortex was removed.

Subsequently, bi-weekly ultrasound monitoring was performed to determine the number of antral follicles present in both the native ovary and the re-implanted ovary to determine the number of antral follicles. The number of antral follicles in both intervention groups was compared and the number of antral follicles in the native ovary was also compared with the reimplanted one in each of the patients.

- Phase 2 Prospective observational study. A cohort of all patients who participated in phase 1 was formed and followed for six months. Those patients who wished to undergo IVF treatment received standard treatment for low responders. The final objective consisted of assessing the gestation rate in both groups, as well as the parameters related to the reproductive technique.

STUDY POPULATION

Patients affected by infertility requiring treatment by IVF or ICSI and who were confirmed low responders based on the inclusion criteria.

INCLUSION CRITERIA (one must be met)

- At least two episodes of poor ovarian response (≤ 3 oocytes retrieved in a conventional scheme).

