- A previous IVF cycle with ≤ 3 oocytes (following a conventional stimulation protocol) and presence of an abnormal ovarian reserve test (antral follicle count of ≤ 5 or AMH ≤ 5 pM).

EXCLUSION CRITERIA (the presence of one excludes from participation)

- Patients older than 40 years.
- Clinical suspicion of endometriosis.

- Anovulatory patient (defined by the presence of irregular cycles and serum progesterone on day 21 of the cycle of ≤ 10 ng/mL).
- Couples with severe male factor: severe oligoasthenozoospermia, oligoasthenoteratozoospermia and azoospermia.
- All patients who do not voluntarily give their express written consent.

STUDY VARIABLES

PHASE 1

- Antral follicle count at randomisation (per ovary).
- Antral follicle count after intervention/control (per ovary, fortnightly for 6 months).
- Determination of AMH and FSH/E₂ at the time of randomisation.
- AMH, FSH/E₂ determination after intervention/control (per ovary, monthly for 6 months).

PHASE 2

- Number of metaphase II oocytes obtained after ovarian stimulation.
- Number of follicles punctured.
- Total number of oocytes obtained after ovarian stimulation.
- Number of fertilised oocytes.
- Evolution of embryo development.
- Serum oestradiol levels on the day of hCG.
- Total dose of FSH used.
- Necessary days of gonadotrophin stimulation.
- Clinical pregnancies (determined as the presence of the sac after embryo transfer).
- Progressive gestations (those exceeding 12 weeks).

5. Methods

ASSESSMENT OF OVARIAN RESERVE

- Basal and follicular serum determination of steroid hormones: serum determinations of FSH, E₂ and AMH) were performed with a microparticle immunoassay kit integrated into the ABBOTT AxSYM® Plus system and 5.20 software (Abbott Laboratories, Abbot Park, IL, USA).

- Ultrasound determinations: antral follicle counting was performed with a GE iVoluson (General Electric, Spain) equipped with 3D vaginal transducer (6.5-9MHz). Antral follicles were counted on day 2-5 of the menstrual cycle.

REMOVAL AND REIMPLANTATION OF THE CORTEX

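### The main outcome is counted fortnightly for six months, but no visit, summary over visits, unit or multiplicity rule is fixed for the between-arm comparison

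*SAP*

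**What the plan says.** - **Objective.** Protocol section 3 gives the main objective as "To assess whether the fragmentation of ovarian cortex increases the pool of antral (potentially stimulable) follicles". It attaches no time point or summary measure.
- **Measurements.** Protocol section 4, Study variables, Phase 1, lists "Antral follicle count at randomisation (per ovary" and "Antral follicle count after intervention/control (per ovary, fortnightly for 6 months", each count being per ovary.
- **Comparisons.** Protocol section 4, Type of study, Phase 1, says "The number of antral follicles in both intervention groups was compared" and adds that "the number of antral follicles in the native ovary was also compared with the reimplanted one in each of the patients". The between-arm comparison comes first and the within-woman one is an addition, so the former is reasonably read as the main one.
- **Design.** Sixty women "will be randomised to two treatment arms after assessment of ovarian reserve". The allocation ratio is not stated.
- **Tests.** The third paragraph of the SAP names a t-test or Mann-Whitney test for quantitative variables, to be chosen as suits the data, and sets the threshold: "Observed differences were considered statistically significant if $p < 0.05". It names no visit, summary, unit, multiplicity rule, paired test or repeated-measures method, and gives AFC at randomisation no part in the treatment contrast.
- **Cycle day.** Protocol section 5, Assessment of ovarian reserve, places antral follicle counting on cycle days 2 to 5, without saying whether this covers the follow-up counts.

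**The concern.** Six months of fortnightly counts give 12 or 13 post-randomisation values per woman. Two analysts who both follow the SAP could answer the main objective from the first visit, the last visit, the most favourable visit or a mean, per ovary or per woman. With one of these fixed in advance, the SAP's tests hold 5% (2.5% for a false increase, the direction the objective names). With none fixed, a reader cannot tell which p-value carries the conclusion or what error rate belongs to it. The unit matters too: counts are made in "number of antral follicles present in both the native ovary and the re-implanted ovary", and two ovaries of one woman are not independent observations.

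A smaller issue is precision. AFC at randomisation is already collected, and in a trial of 60 women using it in the contrast could narrow the interval appreciably.

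**Working it through.** The plan's only error-rate figure is the 0.05 threshold. The sample size of 60 comes with no effect size, SD or power, so there is no calculation to reproduce.

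**Inputs.** From the documents: 60 women, two arms, threshold 0.05, fortnightly counts for 6 months (26 weeks / 2 = 13, or 12 if months are taken as four weeks). Assumed, because the documents give no value: 30 per arm, two-sided tests, normal data with equal SDs, and visit correlation r from 0.3 to 0.9. If counting is confined to cycle days 2 to 5, a 28-day cycle (assumed) leaves about 6 or 7 counts in 6 months.

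**1. Error rate if any significant visit counted as success.** Simulated with no true effect and a two-sample t-test at each visit. Exchangeable means equal correlation between all visits; AR(1) means correlation decaying with time. Repeated runs agree to about one percentage point.

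| Counts, correlation | Either direction, r = 0.3 / 0.5 / 0.7 / 0.9 | False increase, same r |
|---|---|---|
| 12, exchangeable | 40 / 32 / 24 / 14% | 20 / 16 / 12 / 7% |
| 12, AR(1) | 45 / 41 / 35 / 21% | 25 / 22 / 18 / 11% |
| 6, exchangeable | 24 / 21 / 16 / 11% | 12 / 10 / 8 / 6% |
| 6, AR(1) | 26 / 23 / 20 / 13% | 13 / 12 / 10 / 7% |

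The reference values are 5% and 2.5%. As an upper check, 12 independent tests give 1 - 0.95^12 = 46%, and 6 give 1 - 0.95^6 = 26%. Thirteen counts are slightly worse than 12 (exchangeable 42 / 34 / 25 / 14%).

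**2. Precision from baseline AFC.** For a single visit, ANCOVA multiplies the variance by 1 - r², where r is now the correlation of baseline with follow-up: 0.91, 0.75 and 0.51 for r = 0.3, 0.5 and 0.7. Unadjusted, the difference detectable with 80% power is about (2.00 + 0.85) × √(2/30) = 2.85 × 0.258 = 0.74 SD. Multiplying by √0.91, √0.75 and √0.51 gives 0.70, 0.64 and 0.53 SD.

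**3. Choice of window.** Take a true effect of 0.5 SD, 12 visits and adjustment for baseline. Power comes from the noncentral t with 57 df and noncentrality δ / √(2v/30).

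Exchangeable r (baseline included), r = 0.5 / 0.7:
- All-visit mean: v = (1 + 11r)/12 - r² = 0.292 / 0.235.
- Last-6 mean: v = (1 + 5r)/6 - r² = 0.333 / 0.260.
- Effect in the last 6 visits only: δ is 0.25 SD for the all-visit mean, with power 42% / 50%, and 0.5 SD for the last-6 mean, with power 91% / 96%.
- Effect at all visits: all-visit mean 94% / 98%, last-6 mean 91% / 96%.
- Effect in the first 6 visits only: all-visit mean 42% / 50%, last-6 mean 5%.

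AR(1), baseline one interval before the first visit, effect at all visits, r = 0.5 / 0.7:
- All-visit mean: v = 0.215 / 0.329, power 98% / 91%.
- Last-6 mean: v = 0.391 / 0.562, power 86% / 72%.

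Neither window is best in every case. The all-visit mean is safer when the time of onset is unknown, and the documents give no expected onset.

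**The case against.** The strongest reply is that the SAP's tests are valid for any one comparison, that the protocol makes the between-arm comparison the natural main one, and that nothing says every visit is tested. All of this stands. A reader might infer that the plan tests each fortnightly count and so runs an error rate of 40% or more. The documents do not support that: the percentages above describe a best-visit rule that the SAP nowhere states. Nor do they support the reading that the between-arm and within-woman comparisons compete for primacy, since the protocol presents the second as an addition.

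A reader might also infer that ignoring AFC at randomisation invalidates the comparison. It does not. Randomisation keeps the unadjusted test valid, and the gain from adjustment could be small if eligibility based partly on AFC, or surgery on one ovary, weakens the correlation with follow-up.

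It is also fair to say that the number of counts is uncertain: if cycle days 2 to 5 govern follow-up, the inflation at low correlation roughly halves.

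What the reply does not answer is which visit, summary and unit are meant. The SAP's latitude lies between two tests; it selects none of these three.

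**Conclusion.** The gap is real but limited. The between-arm comparison of AFC is reasonably implied as the main analysis, yet its visit or summary, its unit and any multiplicity rule are all left open. The consequence is an undefined error rate for the main conclusion, not a known inflated one. Were any significant visit accepted, the chance of a false difference would be about 14-45% with 12 counts or 11-26% with about 6 (against 5%), and of a false increase about 7-25% or 6-13% (against 2.5%). These figures rest on 30 per arm and visit correlations of 0.3 to 0.9, neither of which the documents give. Omitting baseline AFC is a missed gain in precision and not an error. The point should be fixed because the remedy is cheap.

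**What to change.** In the SAP, define the main between-arm analysis as one test at two-sided 0.05:

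- **Outcome and unit.** Each woman's mean total AFC over all post-randomisation visits. Total means both ovaries in Arm 1, and native plus reimplanted in Arm 2.
- **Model.** ANCOVA on arm, adjusted for total AFC at randomisation, with a rank-based ANCOVA if residuals are clearly non-normal. State the criterion for that switch in advance, since AFC is a small integer count in this population.
- **Window.** A shorter window only if the sponsor justifies it in advance.
- **Missing and affected counts.** Average the available visits. State how missed visits, and counts during ovarian stimulation or pregnancy, are handled; the protocol does not make clear whether the Phase 1 and Phase 2 follow-up periods overlap.
- **Other visits.** Report visit-specific differences with confidence intervals as descriptive.
- **Native versus reimplanted ovary.** Name a paired t-test or Wilcoxon signed-rank test. The SAP's t-test may include the paired form, but this is not stated.
- **Schedule.** Reconcile the cycle-day condition with the fortnightly counts.

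The cost is SAP wording and one model. An isolated significant visit would no longer meet the main objective, and the all-visit mean loses power if the effect is only late. If the data have already been analysed, as the SAP's past tense may suggest, the contrast cannot be called pre-specified: label it post hoc and report every visit.

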In every woman, even in the low responder, there is a pool of dormant (primordial) follicles, not stimulable with gonadotrophins, which, if they could be used would significantly increase the functional reserve of the patient. Aaron Hsueh's research group described a follicular activation technique (Kawamura et al., 2013), which consists of activating these primordial follicles and converting them into antral (stimulable) follicles before the IVF cycle is performed by fragmenting the ovarian tissue. Fragmentation of the ovarian cortex increases actin polymerization and disrupts the intracellular Salvador/Warts/Hippo (SWH) signaling pathway. The SWH pathway is responsible for maintaining proper organ size. Its disruption leads to increased cell growth and survival because CCN (growth factors) and BIRC (inhibitors of apoptosis) levels are increased, resulting in activation of primordial follicles. This explains why the final consequence of ovarian fragmentation is the growth of ovarian primordial follicles and

therefore the generation of a greater number of antral follicles, which are susceptible to stimulation with gonadotrophins, thus potentially increasing the number of mature oocytes that could be obtained in patients undergoing the technique.

From a practical point of view, by laparoscopic surgery, the ovarian cortex is removed, mechanically stimulated in vitro (the cortex is fragmented into multiple aliquots), and then reimplanted, and the conventional IVF cycle is carried out.

This technique was tested in 27 patients with primary ovarian failure (early menopause, the paradigm of ovarian unresponsiveness). The results were as follows: eight patients presented follicular growth, obtaining mature oocytes from five of them and achieving pregnancy in one patient who finally gave birth to a healthy baby. It should be noted that this study was carried out in a "worst-case scenario", in menopausal patients of whom only thirteen had residual follicles in the histological analysis of the pieces, and the eight in whom ovulation was induced belonged to this group, which represents a 62% response to treatment.

2. Hypothesis

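### Where the SAP uses a t-test between arms, it names Student's version, which is safe only with equal arm sizes or equal spreads; the plan secures neither, and Welch's test would remove the dependence at almost no cost

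*SAP*

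**What the plan says.** The third paragraph of the SAP gives one rule for all numerical variables: "Comparison of quantitative variables was performed using the Student's t-test", or the Mann-Whitney test where appropriate. It does not say what makes either test appropriate. The paragraph does separate normal from non-normal variables, but only for descriptive summaries. Unequal variances are not mentioned. On the significance level it says "Observed differences were considered statistically significant if" p is below 0.05, without stating one- or two-sided.

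On group sizes, Protocol section 4 states: "Sixty patients previously confirmed as low responders according to ESHRE criteria will be randomised to two treatment arms after assessment of ovarian reserve". The SAP adds: "The allocation of patients to the study groups was performed using a random number generator", with the numbers kept in a sealed envelope. Neither document gives an allocation ratio, blocks or any other control of arm size. For Phase 2, section 4 says: "Those patients who wished to undergo IVF treatment received standard treatment for low responders". The numbers contributing oocyte, oestradiol, FSH-dose and stimulation-day data therefore depend on patient choice.

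On the likely pattern of response, Protocol section 1 cites an earlier series of 27 women, of whom eight showed follicular growth. It notes that "only thirteen had residual follicles in the histological analysis of the pieces, and the eight in whom ovulation was induced belonged to this group".

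**The concern.** Student's t-test estimates one common variance from both arms. If the spreads differ and the arms are of unequal size, the pooled standard error is wrong. It is too small when the more variable arm is the smaller one, giving too many false positives. It is too large when the more variable arm is the larger one, giving too few.

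Both conditions could arise here. Arm 1 has no intervention. Arm 2 loses an ovary and receives a graft that, on the cited precedent, may work in some women and not in others. A mixture of responders and non-responders is more variable than an untreated group. Loss of the ovary and gain from the graft also act on the mean in opposite directions, so a small mean difference with a wider spread is conceivable. At stake is the accuracy of p-values for every variable sent to the t-test.

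**Working it through.** **Inputs from the documents.** Total 60 in two arms (Protocol section 4); significance level 0.05 (SAP); responders 8 of 27, or 8/13 = 61.5% of those with residual follicles, which matches the 62% in Protocol section 1.

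**Assumptions.** Two-sided test; simple 1:1 randomisation; equal means; normal data in the simulations. The SD ratio r (Arm 2 over Arm 1) is also assumed. An illustrative negative binomial mixture of responders and non-responders gives r of 1.6 to 2.1 with 8/27 responding and 1.1 to 1.4 with 8/13. The documents supply no follicle-count mean or SD to anchor it, so I use it only to justify looking at r from 1.2 to 2.

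**Formula.** With n2 in Arm 2, n1 in Arm 1 and the Arm 1 SD set to 1:

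- true variance of the difference: V = r²/n2 + 1/n1
- variance that Student's test expects: P = [(n2−1)r² + (n1−1)]/(n1+n2−2) × (1/n1 + 1/n2)
- approximate true error = 2 × [1 − Φ(1.96/√(V/P))]

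**Baseline check.** With r = 1, V = P and the error is 5%. Simulation (400,000 trials per cell) gives 4.95 to 5.06% for splits from 30:30 to 20:40.

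**Worked case, Arm 2:Arm 1 = 25:35, r = 2.** V = 4/25 + 1/35 = 0.1886. P = (24×4 + 34)/58 × (1/25 + 1/35) = 2.2414 × 0.06857 = 0.1537. V/P = 1.227 and the error is 7.7%; simulation gives 7.8%.

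| Arm 2:Arm 1 | r | V | P | V/P | Error, formula | Error, simulated |
|---|---|---|---|---|---|---|
| 30:30 | 2 | 0.1667 | 0.1667 | 1.000 | 5.0% | 5.2% |
| 25:35 | 1.2 | 0.0862 | 0.0811 | 1.063 | 5.7% | |
| 25:35 | 1.4 | 0.1070 | 0.0958 | 1.117 | 6.4% | |
| 25:35 | 2 | 0.1886 | 0.1537 | 1.227 | 7.7% | 7.8% |
| 35:25 | 1.2 | 0.0811 | 0.0863 | 0.941 | 4.3% | |
| 35:25 | 2 | 0.1543 | 0.1892 | 0.816 | 3.0% | 3.2% |
| 20:40 | 2 | 0.2250 | 0.1487 | 1.513 | 11.1% | 11.2% |
| 12:24 | 1.4 | 0.2050 | 0.1638 | 1.251 | 8.0% | |
| 12:24 | 2 | 0.3750 | 0.2463 | 1.522 | 11.2% | 11.3% |
| 20:10 | 2 | 0.3000 | 0.4554 | 0.659 | 1.6% | 1.8–2.0% |

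Welch's test, simulated over the same range of splits and SD ratios, stays at about 5%.

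**How likely are uneven arms in Phase 1?** From Binomial(60, 0.5), the smaller arm has 25 or fewer with probability 24.5%, and 20 or fewer with probability 1.35%. Inflation requires Arm 2 to be the smaller arm, which halves these to about 12% and 0.7%. Averaged over all splits, Student's error is 5.1% at r = 1.5 and 5.4% at r = 2.

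**In Phase 2?** Uptake of IVF is not given. If both arms had the same uptake, somewhere between 40 and 80%, the IVF groups would differ by at least 1.5:1 in 18 to 36% of trials and by at least 2:1 in 2 to 12%. With uptake of 50% in one arm and 80% in the other, these become 60% and 28%.

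**The case against.** The case against is substantial, and most of it limits the size of the problem.

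- A reader might infer that Student's test is the only test planned. It is one of two. Follicle counts are small integers in women who may qualify with five or fewer, and could well go to the rank test. This stands. It is not a full escape, because the Mann-Whitney test drifts too: 8.7% or 3.2% at 20:40 or 40:20 with r = 2.
- A reader might infer that this trial's error rate is 2% or 11%. The documents do not support that. Those figures need both a 2:1 split and a doubled SD, and neither is given.
- The 8/27 figure includes 14 menopausal women without residual follicles. The protocol calls that series a worst case, which makes 8/13 arguably the closer precedent and points to r of 1.1 to 1.4. This stands, and it is why the lower rows of the range matter.
- If the procedure has no effect at all, the spreads are equal and Student's test keeps 5%. The distortion needs equal means with unequal spread, and nothing in the documents shows that ovary loss and graft gain cancel. This stands.
- The argument for unequal spread is a skewed mixture, while the simulations use normal data. That is fair, though the large-sample formula depends only on the variances and gives similar answers.
- If "as appropriate" were taken to include a preliminary variance test, the error at r = 2 would be 4.7 to 5.5%. The SAP states no such test.
- The average over splits is close to 5%. That average mixes inflated and deflated errors; the trial has one realised split, and its p-values depend on that split.
- In Phase 2, self-selection is a larger threat than the variance assumption, and Welch's test does nothing about it. This stands.

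None of this shows pooling to be as good as Welch's test here.

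**Conclusion.** The point holds as a specification gap of minor to moderate importance. Wherever the t-test is applied, the plan relies on equal arm sizes or equal spreads and secures neither.

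For a moderately uneven Phase 1 split, the error of a nominal 5% test moves to roughly 6 to 8% or 4 to 3%, depending on which arm is smaller. With near-equal arms or equal spreads it stays at about 5%. Figures near 11% and 2% are the ends of an assumed range and belong mainly to the self-selected Phase 2 groups. All of this rests on assumed SD ratios of 1.2 to 2, equal means and, for Phase 1, simple 1:1 randomisation. The gap itself is certain; its size in this trial is not.

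A reader might also infer that reported confidence limits would be wrong. The SAP plans no confidence intervals, so the point concerns p-values.

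**What to change.** In the third paragraph of the SAP, for between-arm comparisons of means, replace Student's t-test with Welch's (unequal-variance) t-test. Apply it directly, without a preliminary variance test: Welch's test holds its level on its own, so the extra step gains nothing.

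The cost is a short wording change. When the variances are in fact equal, the loss of power is negligible: for an assumed effect of 0.73 SD, 79.6% against 79.7% at 30:30 and 77.5% against 77.7% at 24:36.

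The change leaves the Mann-Whitney option as it is and does not address self-selection into IVF in Phase 2.

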- Other causes: a group of young women with low ovarian response have normal basal FSH hormone levels in whom there is no apparent cause for this response (Tarlatzis et al., 2003). Many hypotheses have been proposed to explain this condition. However, none have been proven: a decrease in the number of FSH receptors available in the granulosa cells, FSH post-receptor defects, etc.

Strategies aimed at improving the management of responding casualties

Efforts to provide better control of responding casualties have currently focused on a priori identification of responding casualties and modification of existing protocols themselves.

A priori identification of responder casualties

- Antral follicle count by transvaginal ultrasound: Antral follicle count is nowadays considered the best predictor of ovarian response in isolation (Broeckmans et al., 2006). Most authors use as a cut-off point 3-4 antral follicles on the day when pituitary suppression is proven.
- FSH elevation at the beginning of the cycle: In disuse because of its variable sensitivity and specificity.
- Maternal age: The probability of not conceiving the first child within one year increases from 5% in women in the 20-30 age group to 30% in women over 35 (Broeckmans et al., 2006).
- Anti-Müllerian hormone (AMH): recently, it has been proposed that the determination of AMH) in blood could be used as a test of ovarian reserve so that decreased levels would indicate ovarian aging. Its efficacy is similar to that of the antral follicle count (Broeckmans et al., 2006).

Therapeutic modifications aimed at reducing the incidence of low response

Since the beginning of ART application, many different protocols have been proposed to manage patients with low response, obtaining very different results in the further studies published, making it very difficult to conclude them. Increasing the dose of FSH used (Tarlaltzis et al., 2003), the use of recombinant FSH instead of purified urinary FSH (Raga et al., 1999), the use of FSH in the luteal phase (Rombauts et al., 1998), modifications in pituitary desensitization protocols (García-Velasco et al. 2000), or pre-treatment with estrogens or combined oral contraceptives (Fanchin et al., 2005), pre-treatment with androgens (Fábregues et al., 2009). The reality is that none of these interventions have been shown to be effective in increasing the gestation rate in the subgroup of low responders.

New strategy for ovulation stimulation

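### Age, which the protocol treats as a predictor of poor response, is neither a study variable nor a covariate: a modest precision loss in Phase 1 and an unseen possible confounder among Phase 2 IVF users

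*SAP*

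**What the plan says.** Protocol section 1 ties age to ovarian response in two places. The consensus definition of low response counts an age of 40 or over as a risk factor. The list of ways to identify low responders in advance includes age, with a figure for conception: "Maternal age: The probability of not conceiving the first child within one year increases from 5% in women in the 20-30 age group", rising to 30% in women over 35. The same list ranks antral follicle count as the best single predictor.

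In section 4, age appears only as an exclusion: "Patients older than 40 years". No lower limit is given. The Phase 1 variables include the antral follicle count at randomisation and then fortnightly for six months, per ovary. The Phase 2 variables include total and metaphase II oocytes. Neither list contains age.

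On design, "Sixty patients previously confirmed as low responders according to ESHRE criteria will be randomised to two treatment arms". The later stage is described as "Phase 2 Prospective observational study", in which only women who wanted IVF were treated and could therefore contribute oocyte data.

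The SAP describes random numbers in sealed envelopes and mentions no stratification. For counts it says "Comparison of quantitative variables was performed using the Student's t-test or U-Mann test, as appropriate", and for categorical outcomes "Comparison of categorical variables was performed using the Chi-square or Fisher test, as appropriate". It names no covariate.

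**The concern.** A factor that the protocol itself regards as prognostic is handled at neither the design nor the analysis stage. The consequences differ by phase.

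In Phase 1, random allocation protects the comparison of follicle counts. Ignoring a prognostic covariate only leaves its variance in the error term. With 60 women and no stated power, some efficiency may be lost that could be had almost free.

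In Phase 2, the women who yield oocytes selected themselves after randomisation. If the choice of IVF depends on age differently in the two arms, the groups will differ in age for reasons other than chance. An unadjusted test would attribute the resulting difference in oocytes to the intervention. Because age is not a listed variable, the planned output would not even reveal the difference.

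**Working it through.** **Inputs from the documents.** 60 women in two arms (Protocol, section 4) and significance at 0.05 (SAP). The sample size cannot be reproduced, because no power, effect size or SD is stated.

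**Assumptions.** 30 per arm and a two-sided test (neither is stated). The age-count correlation ρ, the correlations involving baseline antral follicle count and the number of IVF users per arm are not in the documents, so ranges are shown.

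**Step 1: reference difference.** The difference detectable with 80% power at 30 per arm is (1.960 + 0.842) × √(2/30) = 0.723 SD.

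**Step 2: age alone, Phase 1.** Adjustment multiplies the residual variance by 1 − ρ². Allowing for the extra parameter, the net ratio is (1 − ρ²) × (1 + 1/(60 − 4)). Power for the 0.723 SD difference, before that allowance, is Φ(0.723 / (√(1 − ρ²) × √(2/30)) − 1.960).

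| Assumed ρ (absolute) | Fall in variance | Net variance ratio | Power (80% unadjusted) |
|---|---|---|---|
| 0.1 | 1% | 1.008 | 80.4% |
| 0.2 | 4% | 0.977 | 81.6% |
| 0.3 | 9% | 0.926 | 83.6% |
| 0.4 | 16% | 0.855 | 86.4% |

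**Step 3: age on top of baseline antral follicle count.** Let a be the correlation of baseline count with outcome, b that of age with outcome and c that of age with baseline count. Then R² = (a² + b² − 2abc) / (1 − c²), to be compared with a² for the baseline count alone.

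| a | b | c | R², both | R², count only | Residual variance ratio |
|---|---|---|---|---|---|
| 0.6 | −0.3 | −0.3 | 0.376 | 0.360 | 0.975 |
| 0.6 | −0.3 | −0.2 | 0.394 | 0.360 | 0.947 |
| 0.6 | −0.2 | −0.3 | 0.360 | 0.360 | 0.999 |
| 0.7 | −0.3 | −0.3 | 0.499 | 0.490 | 0.983 |

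Age then removes a further 0% to 5% of residual variance. For comparison, baseline count alone at an assumed 0.6 leaves a variance of 1 − 0.36 = 0.64 and takes the 80% power to about 94%.

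**Step 4: what an age difference among IVF users would do.** An age difference of D (in age SDs) shifts the unadjusted oocyte difference by D × ρ outcome SDs. The false-positive risk given that difference is the chance that a normal variable with mean Dρ/√(2/n) falls beyond ±1.96.

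| D | ρ | Shift (SD) | 15 per arm | 20 per arm | 30 per arm |
|---|---|---|---|---|---|
| 0.25 | 0.1 | 0.025 | 5.1% | 5.1% | 5.1% |
| 0.50 | 0.3 | 0.150 | 7.0% | 7.6% | 8.9% |
| 0.75 | 0.4 | 0.300 | 13.0% | 15.8% | 21.3% |

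These rows show only how the mechanism works. The documents give no basis for choosing D, ρ or n.

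**Step 5: cost of adjusting.** One extra parameter costs about 1/(N − 4) of variance: 1/56 = 1.8% with 60 women, 1/36 = 2.8% with 40 IVF users and 1/26 = 3.8% with 30.

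**The case against.** The strongest reply is that this is a small matter resting on assumed numbers. Much of that stands. Four stronger readings are tempting, and the documents support none of them.

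- **That the main follicle comparison is biased.** It is randomised, so the unadjusted test is valid and adjustment is a choice about efficiency.
- **That chance age imbalance among IVF users is bias.** If the groups behaved as random samples, a gap of half an age SD or more would occur with probability 11% at 20 per arm and 17% at 15. That variation is already in the unadjusted standard error, and averaged over it the error rate stays at 5%. Only imbalance produced by self-selection is a bias, and no figure in oocytes can be put on it.
- **That the rise from 5% to 30% shows a large age effect on counts.** The figure concerns failure to conceive within a year. The documents quantify no effect of age on follicle or oocyte numbers, and the limit at 40 truncates the age range, which may weaken any such effect.
- **That age is the main covariate missing from the plan.** For precision in the follicle comparison, the baseline antral follicle count matters more. It is already recorded and equally unused.

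Nor does the missing list entry show that age was never recorded, since the exclusion cannot be applied without it. Finally, adjusting for age cannot remove selection on other factors. None of this shows that adjustment would do harm beyond a small loss of precision, or that another section already provides it.

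**Conclusion.** The gap is real and modest. Age is treated as prognostic in the background, is needed for eligibility and is then absent from the study variables and from every analysis.

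For Phase 1 the consequence is limited to precision. On assumed correlations of 0.1 to 0.4, the result ranges from no net gain to a 16% fall in variance (about 14% net). Beside baseline antral follicle count the further fall of 0% to 5% may be largely or wholly offset by the cost of about 2%.

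For Phase 2 the point is stronger in kind but cannot be sized. The oocyte comparison is open to confounding by age through the choice of IVF, and the plan neither displays nor corrects it. Whether such a difference exists is unknown from the documents. The change should be made because it costs little and makes the Phase 2 comparison interpretable, not because a material error has been shown.

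**What to change.** - Add age at randomisation to the study variables.
- Compare antral follicle, total oocyte and metaphase II counts with a model containing arm, baseline antral follicle count and age as a continuous covariate. For the fortnightly follicle counts, prespecify one time point or use a repeated-measures model.
- Report each adjusted difference with its 95% CI beside the unadjusted one.
- Show age by arm, both overall and among IVF users.
- Leave the pregnancy comparison unadjusted, because events will be few. Even at the top of the 0% to 18% range that the protocol cites for low responders, and with every woman treated, 0.18 × 60 is about 11 pregnancies.
- State that age adjustment does not remove selection on other factors among IVF users.
- The SAP describes allocation and analysis in the past tense. If the data have already been analysed, label the adjusted results post hoc.

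The cost is SAP wording, one model per count outcome and one degree of freedom for age (about 2% of variance with 60 women, 3% to 4% with 30 to 40 IVF users). It needs no extra visit, patient or measurement.
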